## 739 **11.10 PREGNANCY REPORTING**

740 If pregnancy occurs, the participant will be discontinued from the study. The occurrence of  
741 pregnancy will be reported on an AE Form.

## 742 **11.11 TIMING OF EVENT REPORTING**

743 SAEs and UADEs must be recorded within 24 hours via completion of the serious adverse event  
744 form and sponsor notification.

745 Other reportable adverse events, device malfunctions (with or without an adverse event), and  
746 device complaints should be reported promptly by completion of the relevant case report form,  
747 but there is no formal required reporting period.

748 The principal investigator is responsible for reporting serious study-related adverse events and  
749 abiding by any other reporting requirements specific to the Institutional Review Board or Ethics  
750 Committee.

751 Upon receipt of a UADE report, the study principal investigators will investigate the UADE and  
752 if indicated, report the results of the investigation to the sites' IRBs, and the Sponsor (Tandem  
753 Diabetes Care) within ten working days of becoming aware of the UADE per 21CFR 812.46(b)

754 (2). The Sponsor must determine if the UADE presents an unreasonable risk to participants. If  
755 so, all investigations, or parts of investigations presenting that risk, will be terminated as soon as  
756 possible but no later than 5 working days after the Sponsor makes this determination and no later  
757 than 15 working days after first receipt notice of the UADE.

758 In the case of a device system component malfunction (e.g. pump, CGM, control algorithm),  
759 information will be forwarded to the responsible company by the site personnel, to be handled  
760 by its complaint management system.

## 761 **11.12 PARTICIPANT DISCONTINUATION OF STUDY DEVICE**

762 Rules for discontinuing study device use are described below.

- 763 1) The investigator believes it is unsafe for the participant to continue on the intervention.  
*764 This could be due to the development of a new medical condition or worsening of an  
765 existing condition; or participant behavior contrary to the indications for use of the  
766 device that imposes on the participant's safety*
- 767 2) The participant requests that the treatment be stopped
- 768 3) Participant pregnancy  
*769 If pregnancy occurs, the participant will be discontinued from the study entirely.  
770 Otherwise, even if the study device system is discontinued, the participant will be  
771 encouraged to remain in the study through the final study visit.*
- 772 4) Two distinct episodes of DKA as defined in section 11.4
- 773 5) Two distinct episodes of severe hypoglycemia as defined in section 11.3
- 774 6) The investigator may have a subject temporarily stop use of Control-IQ during: periods  
775 of significant illness, temperature >101.5, use of oral or injectable glucocorticoids, use of  
776 epinephrine for the emergency treatment of a severe allergic reaction or asthma attack, or  
777 if a subject is going to the hospital for any reason. If the investigator believes the period of  
778 illness may be prolonged or put the safety of the subject or the overall study at risk, the  
779 investigator may withdraw the subject from the study.

## 780 **11.13 CRITERIA FOR SUSPENDING OR STOPPING OVERALL 781 STUDY**

- 782 1) In the case of a system malfunction resulting in a severe hypoglycemia or severe  
783 hyperglycemia event (as defined in sections 11.3 and 11.4), use of the study device  
784 system will be suspended while the problem is diagnosed.
- 785 2) Three or more cases of severe hypoglycemia or three or more cases of severe  
786 hyperglycemia (as defined in sections 11.3 and 11.4) across the entire study.
- 787 3) In addition, study activities could be similarly suspended if the manufacturer of any  
788 constituent study device requires stoppage of device use for safety reasons (e.g. product  
789 recall). The affected study activities may resume if the underlying problem can be  
790 corrected by a protocol or system modification that will not invalidate the results  
791 obtained prior to suspension.

792 The Sponsor (Tandem Diabetes Care) will be informed of all serious adverse events and  
793 any unanticipated adverse device events that occur during the study and will review  
794 compiled safety data at periodic intervals. The Sponsor will request suspension of study  
795 activities or stoppage of the study if deemed necessary based on the totality of safety data  
796 available.

797 **11.14 SAFETY OVERSIGHT**

798 The clinical site principal investigator will review all reported adverse events and adverse device  
799 effects, and report them to the study sponsor.

800 As this is a single site clinical feasibility study, the Medical Director from the study sponsor will  
801 carefully review all adverse event reports, and adjudicate their relationship the study device  
802 based on the site principal investigator's report and all available information.

803

804

---

Confidential

*Contains trade secrets and/or confidential information exempt from disclosure from 21 CFR 20.61*

805 **12 MISCELLANEOUS CONSIDERATIONS**

806 **12.1 DRUGS USED AS PART OF THE PROTOCOL**

807 Participants will use either lispro or aspart insulin prescribed by their personal physician.  
808 Participants not using lispro or aspart insulin at the time of screening may not start use of the  
809 study device until they have one of these insulins available to them for use.

810 **12.2 PROHIBITED MEDICATIONS, TREATMENTS, AND**  
811 **PROCEDURES**

812 Participants using other insulins at the time of enrollment will be asked to contact their personal  
813 physician to change their prescribed personal insulin to lispro or aspart for the duration of the  
814 trial.

815 Treatment with any non-insulin glucose-lowering agent other than metformin (including GLP-1  
816 agonists, Symlin, DPP-4 inhibitors, SGLT-2 inhibitors, sulfonylureas and naturaceuticals) or  
817 AfreZZa will not be permitted during the trial.

818 The investigational study devices (study insulin pump, study phone, study CGM systems) must  
819 be removed before Magnetic Resonance Imaging (MRI), Computed Tomography (CT) or  
820 diathermy treatment. Participants may continue in the trial after temporarily discontinuing use if  
821 requiring one of the treatments above.

822 **12.3 PARTICIPANT COMPENSATION**

823 Participant compensation will be specified in the informed consent form.

824 **12.1 PARTICIPANT ACCESS TO STUDY DEVICE AT STUDY**  
825 **CLOSURE**

826 Participant will return all study devices and supplies (insulin pump, CGM and related supplies)  
827 at study closure. Participant may keep the study ketone meter and study glucometer if these  
828 devices are not marked for investigational use only.

829

830

831 **13 DATA COLLECTION AND MONITORING**

832 **13.1 CASE REPORT FORMS AND DEVICE DATA**

833 The main study data are collected through a combination of paper/electronic case report forms  
834 (CRFs) and electronic device data files obtained from the study software and individual  
835 hardware components. These electronic device files and paper/electronic CRFs are considered  
836 the primary source documentation.

837 When data are directly collected in electronically, this will be considered the source data. The  
838 clinical site will maintain appropriate medical and research records for this trial, in compliance  
839 with ICH E6 and regulatory and institutional requirements for the protection of confidentiality of  
840 participants.

841 Whenever possible, data will be directly collected in electronic form, which will be considered  
842 the source data. Otherwise the paper case report forms will be considered the source data.

843 **13.2 STUDY RECORDS RETENTION**

844 Study documents should be retained for a minimum of 2 years after the last approval of a  
845 marketing application in an ICH region and until there are no pending or contemplated marketing  
846 applications in an ICH region or until at least 2 years have elapsed since the formal  
847 discontinuation of clinical development of the investigational product. These documents should  
848 be retained for a longer period, however, if required by local regulations. No records will be  
849 destroyed without the written consent of the sponsor, if applicable. It is the responsibility of the  
850 sponsor to inform the investigator when these documents no longer need to be retained.

851 **13.3 PROTOCOL DEVIATIONS**

852 A protocol deviation is any noncompliance with the clinical trial protocol, GCP, or procedure  
853 requirements. The noncompliance may be either on the part of the participant, the investigator, or  
854 the study site staff. As a result of deviations, corrective actions are to be developed by the site  
855 and implemented promptly. The site PI/study staff is responsible for knowing and adhering to  
856 their IRB reporting requirements.

857 **13.4 ETHICAL STANDARD**

858 The investigator will ensure that this study is conducted in full conformity with Regulations for  
859 the Protection of Human Participants of Research codified in 45 CFR Part 46, 21 CFR Part 50,  
860 21 CFR Part 56, and/or the ICH E6.

861 **13.5 INSTITUTIONAL REVIEW BOARDS**

862 The protocol, informed consent form(s), recruitment materials, and all participant materials will  
863 be submitted to the IRB for review and approval. Approval of both the protocol and the consent  
864 form must be obtained before any participant is enrolled. Any amendment to the protocol will  
865 require review and approval by the IRB before the changes are implemented to the study. All  
866 changes to the consent form will be IRB approved; a determination will be made regarding  
867 whether previously consented participants need to be re-consented.

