### 226 **5.3 STUDY ENDPOINTS**

227 1) Primary Endpoint:

- 228 a. To demonstrate the safety of the system, by assessing the number of severe  
229 hypoglycemic events (needing assistance) compared to expected incidence

230 2) Secondary Endpoints:

- 231 a. Time in range 70-180 mg/dL
- 232 b. Time < 54 mg/dL
- 233 c. Time < 70 mg/dL
- 234 d. Time > 180 mg/dL
- 235 e. Time > 250 mg/dL
- 236 f. Time in tight glycemic range 70-140 mg/dL
- 237 g. Post-prandial glycemic peak
- 238 h. 4-hour post meal glucose AUC
- 239 i. Sensor glucose median and interquartile range
- 240 j. CGM metrics daytime vs. nighttime
- 241 k. CGM metrics compared each week after adaptation
- 242 l. DKA
- 243 m. Serious Adverse Events
- 244 n. Adverse Device Effects
- 245 o. Change in total daily insulin use, basal and bolus
- 246 p. Number of physician overrides/physician initiated changes in pump settings
- 247 q. Patient Reported Outcomes

248 **6 SUBJECT SELECTION**

249 **6.1 SUBJECT POPULATION**

250 **6.1.1 INCLUSION CRITERIA:**

251 Eligibility to enroll in the study will be assessed based on the following inclusion criteria:

- 252 1) Adult subjects  $\geq$  age 18 years
- 253 2) Clinical diagnosis of type 1 diabetes for at least one year
- 254 3) Using a basal/bolus regimen by injection (MDI therapy)
- 255 4) Total daily dose  $\geq$  10 units/day
- 256 5) Willing to use only aspart (novolog) or lispro (humalog) U-100 insulin with the study  
257 pump.
- 258 6) A1c  $\geq$  7.5% and  $\leq$  11% at screening
- 259 7) Not pregnant or planning a pregnancy during the time period of the study.
- 260 8) Has current glucagon product to treat severe hypoglycemia (injectable or nasal) at home  
261 (will provide prescription if they do not have one)
- 262 9) Willingness to follow study procedures and a signed informed consent form

263 **6.1.2 EXCLUSION CRITERIA:**

264 Eligibility to enroll in the study will be assessed based on the following exclusion criteria:

- 265 1) Two or more episodes of severe hypoglycemia (needing assistance) in the past 6 months
- 266 2) Two or more episodes of diabetic ketoacidosis in the past 6 months
- 267 3) Inpatient psychiatric treatment in the past 6 months
- 268 4) History of drug abuse (defined as any illicit drug use) or history of alcohol abuse prior to  
269 screening or unwillingness to agree to abstain from illicit drugs throughout the study
- 270 5) Significant chronic kidney disease or hemodialysis
- 271 6) Significant liver disease

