## 409 **7.8 POST STUDY PHONE CALL**

410 All participants will have a post-study phone call 3 ( $\pm 1$ ) days after the date of their final visit and  
411 transition back to their prior insulin therapy, during which the following will occur:

412 • Check on transition back to usual home diabetes care

413 • Assessment of adverse events

414

---

Confidential

Contains trade secrets and/or confidential information exempt from disclosure from 21 CFR 20.61

415 **8 STATISTICAL CONSIDERATIONS**

416 **8.1 STATISTICAL ANALYSIS:**

417 This feasibility study is a prospective, single arm study, evaluating al algorithm to recommend  
418 insulin pump settings at pump start (initialization) and then weekly for 13 weeks.

419 Descriptive statistics of the rates of severe hypoglycemia, DKA, and serious adverse events will  
420 be reported for baseline (with CGM run-in data) and compared to changes after each weekly  
421 adaptation. Additionally, descriptive statistics of glycemic outcomes will for baseline and each  
422 intervention configuration will be provided.

423 The statistics will include all primary and secondary outcomes of the study as listed in section  
424 5.3. These statistics will be calculated at the patient-level, and a sub-analysis of daytime vs.  
425 nighttime statistics will be provided.

426

427

428 **9 RISKS AND BENEFITS**

429 **9.1 POTENTIAL RISKS AND BENEFITS OF THE DEVICE**

430 Risks and Benefits are detailed below. Loss of confidentiality is a potential risk; however, data  
431 are handled to minimize this risk. Hypoglycemia, hyperglycemia and ketone formation are  
432 always a risk in participants with diabetes and participants will be monitored for this.

433 **9.2 VENIPUNCTURE RISKS**

434 A hollow needle/plastic tube may be placed in the arm for taking blood samples. Blood draws  
435 can cause some common reactions like pain, bruising, or redness at the sampling site. Less  
436 common reactions include bleeding from the sampling site, formation of a small blood clot or  
437 swelling of the vein and surrounding tissues, and fainting.

438 **9.3 FINGERSTICK RISKS**

439 About 1 drop of blood will be removed by fingerstick for measuring blood glucose and  
440 sometimes Hemoglobin A1c (HbA1c) or other tests. This is a standard method used to obtain  
441 blood for routine hospital laboratory tests. Pain is common at the time of lancing. In about 1 in  

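### The primary endpoint and the three-case suspend-or-stop criterion count the same severe hypoglycemia events, and section 8.1 has no estimate or interval that allows for this

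*Combined protocol and SAP*

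**What the plan says.** **Primary endpoint (5.3).** The wording is "To demonstrate the safety of the system, by assessing the number of severe" hypoglycemic events, compared with an expected incidence. The documents never give that incidence, nor a margin or success criterion.

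**Study-level rule (11.13).** The section heading is "CRITERIA FOR SUSPENDING OR STOPPING OVERALL" the study. Item 2 reads "Three or more cases of severe hypoglycemia or three or more cases of severe" "hyperglycemia (as defined in sections 11.3 and 11.4) across the entire study". The item names no action. It is a raw count, the same for 20 or 30 users and for an early or late third case, with no stated probability of being met. Item 3, on manufacturer stoppages, adds "The affected study activities may resume if the underlying problem can be" corrected; whether this also covers item 2 is not said. The sponsor also reviews "compiled safety data at periodic intervals. The Sponsor will request suspension of study" activities or stoppage on the totality of the safety data.

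**Analysis (8.1).** "Descriptive statistics of the rates of severe hypoglycemia, DKA, and serious adverse events will" be reported for baseline and compared after each weekly adaptation. There is no interval, no person-time rule and no reference to 11.13.

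**Population (6.1.2 item 1).** The exclusion is "Two or more episodes of severe hypoglycemia (needing assistance) in the past 6 months", so one recent episode is allowed.

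**Size and duration (synopsis).** The goal is 30 subjects starting the device and at least 20 completing, with 13 weeks of use.

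**The concern.** The variable that can halt the study is the variable the study is meant to estimate. When a count is both the endpoint and the stopping criterion, the simple count and the simple rate depend on how the study ended as well as on the underlying risk. A study that reaches week 13 has been selected for few events; one halted at its third event has had its person-time cut off exactly at an event. Section 8.1 treats both alike.

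At stake is the reading of the primary result. The endpoint invites a direct comparison of a count with an expectation. Without an interval, a completed study with one or two events could be presented as showing safety when the data are compatible with a much higher rate. A study that ended at the third event would be summarised by a rate that is biased against the system.

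**Working it through.** The plan has no sample-size or operating-characteristic figure to reproduce. The calculation below is conditional on reading item 2 as ending exposure at the third SH event.

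**Inputs**
- Users: 20 (minimum completing) to 30 (goal starting), from the synopsis.
- Exposure T: 20 × 13/52 = 5.0 person-years; 30 × 13/52 = 7.5 person-years.
- True SH rate λ: not in the documents. Assumed range 0.1 to 0.4 per person-year.
- Events: Poisson with mean m = λT.

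**1. How often the third event occurs.** P(X ≥ 3) = 1 − e^(−m)(1 + m + m²/2).

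| λ per person-year | T = 5.0 | T = 7.5 |
|---|---|---|
| 0.1 | 1% | 4% |
| 0.2 | 8% | 19% |
| 0.3 | 19% | 39% |
| 0.4 | 32% | 58% |

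Allowing for clustering within subjects (negative binomial, assumed per-subject dispersion 0.2), the T = 7.5 figures at 0.2 and 0.4 become 20% and 53%.

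**2. Completed studies.** The mean rate given completion is E(X | X ≤ 2)/T. With T = 7.5:
- λ = 0.2: 1.034/7.5 = 0.14.
- λ = 0.4: 1.412/7.5 = 0.19.

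**3. All studies, plain events/person-time.** Completed studies contribute [P(1) + 2P(2)]/T. For studies stopped at time t, the estimate is 3/t. Integrating over the gamma density of the third event time gives a contribution of 1.5λ·P(X ≥ 2). With T = 7.5:
- λ = 0.2 (m = 1.5): (0.335 + 2 × 0.251)/7.5 + 0.3 × 0.442 = 0.112 + 0.133 = 0.24.
- λ = 0.4 (m = 3): (0.149 + 2 × 0.224)/7.5 + 0.6 × 0.801 = 0.080 + 0.481 = 0.56.

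So the plain rate is too low among completed studies and too high on average overall. Simulation gives the same averages to within 0.002.

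**4. What a low count can exclude.** The exact two-sided 95% Poisson upper limit for k events is χ²(0.975; 2k + 2)/2, divided by T = 7.5:

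| Events | Upper limit, events | Upper limit, per person-year |
|---|---|---|
| 0 | 3.69 | 0.49 |
| 1 | 5.57 | 0.74 |
| 2 | 7.22 | 0.96 |

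None of these excludes a mean of 3 events.

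**5. An interval that fits the stop.** If exposure ends at the third event after t person-years, 2λt follows a chi-square distribution with 6 degrees of freedom, so the 95% limits for λ are 0.619/t and 7.22/t. Using these when stopped and the exact Poisson limits when completed gave about 97.5% simulated coverage at λ = 0.2 and 0.4 with T = 7.5: conservative, but valid.

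**The case against.** A reader might infer that the rule caps the primary endpoint at two events and makes the study look safe by construction. The documents do not support that.

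- **The cap is not in the text.** The 11.13 heading covers suspending as well as stopping, item 2 has no verb, item 1 describes a suspension pending diagnosis, and resumption is mentioned under item 3. A suspended and resumed study could finish with three or more events. If a case means a participant, events could also exceed two without meeting the rule.
- **A count below expectation is automatic only if about three or more events were expected.** Three expected events needs 3/7.5 = 0.40 per person-year with 30 users or 3/5.0 = 0.60 with 20. Allowing one prior episode does not establish such a rate. At 0.75 expected events (0.1 per person-year, 30 users), a completed study falls below expectation only 49% of the time.
- **No decision rule says that a low count means safe.** Section 8.1 is descriptive. At a mean of 3 the rule would be met in 58% of studies, which is a visible signal. The plan retains data from withdrawn subjects, and nothing says data before a stop would be dropped.
- **Nothing says a stopped study would be set against planned rather than accrued exposure.** Section 8.1 speaks of rates, though it gives no denominator.

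A count-based safety rule is also an ordinary choice in a single-site feasibility study, and the missing expected incidence is the more basic gap. All of this stands and limits the point to its conditional form. It does not remove it: once an expected incidence is supplied, the comparison still needs a denominator and an interval that fit how exposure ended.

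**Conclusion.** The concern holds in conditional form. The endpoint and item 2 count the same event, 8.1 takes no account of this, and the text leaves open whether item 2 means suspension or stop. If it ends exposure, completed studies understate the rate (0.14 and 0.19 for assumed truths of 0.2 and 0.4), and the plain rate over all studies overstates it (0.24 and 0.56). These figures rest on a Poisson model, 7.5 person-years and assumed rates, and the distortion is smaller at lower rates.

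The limited evidence in a low count does not depend on how item 2 is read: for any study completing 7.5 person-years, upper limits of 0.49 to 0.96 per person-year for 0 to 2 events are too wide for the count alone to demonstrate safety. This should be corrected, but it does not show that the design guarantees a favourable answer.

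**What to change.** **In 8.1:**
- Report SH events over the on-device person-time actually accrued, and compare them with the expected incidence multiplied by that person-time. This requires the sponsor to state the expected incidence and its source.
- Give an exact 95% interval matched to how exposure ended:
  - study completes: exact Poisson limits;
  - exposure ends at the third event: chi-square (gamma) limits on the person-time to that event;
  - study is suspended and resumed: include events and person-time after resumption, with exact Poisson limits on the total.
- Base any safety conclusion on the upper limit, not on the count being below expectation.

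**Across 5.3, 8.1 and 11.13:** reconcile whether item 2 means suspension or stop, whether the resumption clause covers it, and whether cases are events or participants. The clinical threshold is for the sponsor and is not questioned here.

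**Cost:** a few sentences, with no extra subjects, visits or procedures. The downside is a less favourable reading of a completed study with two or fewer events.

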583 Adverse Event (AE): Any untoward medical occurrence in a study participant, irrespective of the  
584 relationship between the adverse event and the device(s) under investigation (see section 11.2 for  
585 reportable adverse events for this protocol).

586 Serious Adverse Event (SAE): Any untoward medical occurrence that:

587 Results in death.

588 Is life-threatening; (a non-life-threatening event which, had it been more severe, might have  
589 become life-threatening, is not necessarily considered a serious adverse event).

590 Requires inpatient hospitalization or prolongation of existing hospitalization.

591 Results in persistent or significant disability/incapacity or substantial disruption of the ability to  
592 conduct normal life functions (sight threatening).

593 Is a congenital anomaly or birth defect.

594 Is considered a significant medical event by the investigator based on medical judgment (e.g.,  
595 may jeopardize the participant or may require medical/surgical intervention to prevent one of the  
596 outcomes listed above).

597 Unanticipated Adverse Device Effect (UADE): Any serious adverse effect on health or safety or  
598 any life-threatening problem or death caused by, or associated with, a device, if that effect,  
599 problem, or death was not previously identified in nature, severity, or degree of incidence in the  
600 investigational plan or application (including a supplementary plan or application), or any other  
601 unanticipated serious problem associated with a device that relates to the rights, safety, or  
602 welfare of participants (21 CFR 812.3(s)).

603 Adverse Device Effect (ADE): Any untoward medical occurrence in a study participant which  
604 the device may have caused or to which the device may have contributed (Note that an Adverse  
605 Event Form is to be completed in addition to a Device Deficiency or Issue Form).

606 Device Complaints and Malfunctions: A device complication or complaint is something that  
607 happens to a device or related to device performance, whereas an adverse event happens to a  
608 participant. A device complaint may occur independently from an AE, or along with an AE.  
609 An AE may occur without a device complaint or there may be an AE related to a device  
610 complaint. A device malfunction is any failure of a device to meet its performance specifications  
611 or otherwise perform as intended. Performance specifications include all claims made in the  

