## 660        **11.5 RELATIONSHIP OF ADVERSE EVENT TO STUDY DEVICE**

661        The study investigator will assess the relationship of any adverse event to be related or unrelated  
662        by determining if there is a reasonable possibility that the adverse event may have been caused  
663        by the study device.

664        To ensure consistency of adverse event causality assessments, investigators should apply the  
665        following general guideline when determining whether an adverse event is related:

666        Yes

667        There is a plausible temporal relationship between the onset of the adverse event and the study  
668        intervention, and the adverse event cannot be readily explained by the participant's clinical state,  
669        intercurrent illness, or concomitant therapies; and/or the adverse event follows a known pattern  
670        of response to the study intervention; and/or the adverse event abates or resolves upon  
671        discontinuation of the study intervention or dose reduction and, if applicable, reappears upon  
672        re-challenge.

673        No

674        Evidence exists that the adverse event has an etiology other than the study intervention (e.g.,  
675        preexisting medical condition, underlying disease, intercurrent illness, or concomitant  
676        medication); and/or the adverse event has no plausible temporal relationship to study  
677        intervention.

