## 689 **11.7 CODING OF ADVERSE EVENTS**

690 Adverse events will be coded using the MedDRA dictionary. The investigator's assessment will  
691 be recorded.

692 Adverse events that continue after the participant's discontinuation or completion of the study  
693 will be followed until their medical outcome is determined or until no further change in the  
694 condition is expected.

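### The plan names two assessors of device relatedness and does not say whose call defines the Adverse Device Effects endpoint

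*Combined protocol and SAP*

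**What the plan says.** Section 5.3 lists "Adverse Device Effects" among the secondary endpoints (item n there, item m in the synopsis). Section 8.1 promises descriptive statistics for every outcome in 5.3. Section 11.1 defines an ADE as an untoward medical occurrence that "the device may have caused or to which the device may have contributed".

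Two sections assign the causality judgement:

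- Section 11.5: "The study investigator will assess the relationship of any adverse event to be related or unrelated". It adds guidelines for answering yes or no. On the same subject, section 11.7 says "The investigator's assessment will" be recorded.
- Section 11.14: the site principal investigator reviews all reported adverse events and ADEs and reports them to the sponsor. Then "the Medical Director from the study sponsor will" "carefully review all adverse event reports, and adjudicate their relationship the study device", "based on the site principal investigator's report and all available information". The stated reason is that this is a single-site feasibility study.

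The sponsor also develops and manufactures the insulin pump system (section 4.2).

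**The concern.** The ADE count depends on a causality judgement, so the person whose judgement is used determines the result. The plan names two people and gives no order of precedence. To adjudicate ordinarily means to decide, and the adjudicator may use information beyond the investigator's report. One available reading is therefore that the second call supersedes the first.

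The second assessor works for the manufacturer. The study has a single arm, so no control group would reveal a lean in attribution. Attribution is also open to honest disagreement here: section 9.10 notes that mild hypoglycemia and hyperglycemia are frequent in type 1 diabetes itself. What is at stake is whether the published ADE figure can be reproduced from the plan, and whether a reader could see that it rests on the manufacturer's view where the investigator thought otherwise.

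**Working it through.** The documents give no ADE figure, expected rate or threshold, so there is nothing to reproduce. The check is textual.

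**Step 1. Does the endpoint depend on relatedness?** Yes. Under 11.1, possible causation by or contribution from the device is what makes an adverse event an ADE.

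**Step 2. Who makes the call?** The investigator under 11.5; the sponsor's Medical Director under 11.14.

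**Step 3. Is there a rule for disagreement?** Sections 5.3, 8.1, 11.1, 11.2, 11.4, 11.5, 11.7, 11.13 and 11.14 contain none. Section 11.7 preserves the investigator's assessment but does not name it as the value for the endpoint. Section 8.1 does not mention assessors. No independent adjudicator or events committee is described.

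**Step 4. What does the gap do to the count?** Let *a* be the events both assessors call ADEs, *b* those only the investigator does, and *c* those only the Medical Director does.

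| Rule for the endpoint | ADE count |
|---|---|
| Investigator's call governs | a + b |
| Medical Director's call governs | a + c |
| Either call suffices | a + b + c |

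The first two rules differ by (a + c) − (a + b) = c − b, which can have either sign. All three are compatible with the present text. If the calls never differ, b = c = 0 and the rules agree.

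**Step 5. Is the threshold the same for both?** Not clearly. The 11.1 definition asks whether the device may have caused or contributed. The first route to a yes in 11.5 also requires that the event not be readily explained by the participant's clinical state, intercurrent illness or other therapy. Section 11.1 does not refer to 11.5, and 11.14 does not say which standard the adjudicator applies.

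**Step 6. What lies outside the gap?** Severe hypoglycemia (11.3), DKA (11.4) and SAEs (11.1) are defined without a relatedness call. The criterion of three or more cases in 11.13 uses the definitions in 11.3 and 11.4 and so does not need one either.

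**Step 7. Can it be sized?** No. Neither *b* nor *c* can be derived from the documents, and a rate would need assumed event counts.

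**The case against.** The strongest reply is that silence on precedence is not a grant of power. Section 11.14 does not say that the Medical Director's view replaces the investigator's, that it defines the endpoint, or that it can only reduce the count. It draws on the investigator's report and could add events. The investigator's assessment is recorded, so a reversal should be traceable. Sponsor review is explained by the single-site feasibility design, and the absence of an independent committee is a design choice. All of this stands, and it limits the point to a missing rule.

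Three stronger readings are tempting and are not supported:

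- *The manufacturer decides which events count.* The text permits that reading but does not state it.
- *The adjudication controls what is recorded.* A reader might infer this because 11.2 to 11.4 make some glucose events reportable only when associated with an ADE. But section 7.4 requires an adverse event form for every event a subject reports, 11.1 requires one for an ADE alongside the device form, and under 11.14 the site reviews and forwards events before the Medical Director sees them. No passage lets the adjudication delete a form.
- *The study's main safety conclusion is exposed.* The primary objective rests on severe hypoglycemia, which needs no relatedness call.

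The reply does not remove the gap. Traceability in source records is not disclosure in the results, and the single-site rationale explains who reviews, not which call is tabulated.

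**Conclusion.** The point holds in a limited form. Two assessors are named for the judgement that defines the ADE endpoint, no rule says whose call is used, and nothing requires disagreements to be shown. The ADE count therefore cannot be reproduced from the plan whenever the assessors differ.

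The consequence is confined to one descriptive secondary endpoint, and its size cannot be calculated. The conclusion assumes only that the two assessors may sometimes disagree and that no other study document in force sets the precedence. It does not assume that the sponsor would downgrade events. The change is worth making because it is cheap and replaces an open-ended adjudication by the manufacturer with a rule less prone to bias in a single-arm study.

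**What to change.** State in 11.14 and 5.3, with matching text in the synopsis, that an event counts toward the endpoint if either the investigator or the sponsor's Medical Director judges that the device may have caused or contributed to it. That is the 11.1 threshold, and it should be named as the one both assessors apply for this endpoint. Sponsor review could then add an ADE but not remove one the investigator attributed to the device.

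Identify the endpoint as Adverse Device Effects, not by its letter: item n is ADEs in 5.3 but Serious Adverse Events in the synopsis. Tabulate both assessments and list every disagreement.

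The cost is two sentences, the matching synopsis edit and one listing, with no added staff or committee. The downside is that the reported ADE count may be slightly higher: in the notation above, by *c* compared with the investigator's call alone, or by *b* compared with the Medical Director's.
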